7.4 Analysis of Vital Signs and Weight

Vital sign variables are body temperature, sitting systolic blood pressure, sitting diastolic blood pressure, sitting pulse rate, and body weight.

The criteria for potentially clinically significant vital sign findings are presented in [Table 2](#).

Table 2. Criteria for Potentially Clinically Significant Vital Sign Values

Test/Measurement	Very Low (VL)	Very High (VH)
Systolic Blood Pressure	≤ 90 mmHg AND A decrease of ≥ 20 mmHg from baseline	≥ 180 mmHg AND An increase of ≥ 20 mmHg from baseline
Diastolic Blood Pressure	≤ 50 mmHg AND A decrease of ≥ 15 mmHg from baseline	≥ 105 mmHg AND An increase of ≥ 15 mmHg from baseline
Pulse Rate	≤ 50 bpm AND A decrease of ≥ 15 bpm from baseline	≥ 120 bpm AND An increase of ≥ 15 bpm from baseline
Weight	A decrease of ≥ 15% from baseline	An increase of ≥ 15% from baseline
Body Temperature		> 38.3°C AND An increase of ≥ 1.1°C from baseline

The baseline value for vital signs will be the last measurement on or before the day of the first dose of study drug. The same baseline value will be used for change to Treatment Period visits and change to Post-Treatment Period visits.

Mean changes from baseline to each post-baseline visit, including applicable post treatment visits, will be summarized. Each vital sign parameter will be summarized with the baseline mean, visit mean, change from baseline mean, standard deviation, minimum, median, and maximum.

The number and percentage of subjects with on-treatment values meeting the specified criteria for Potentially Clinically Significant (PCS) vital sign values (Table 2) will be summarized. A post-baseline value must be more extreme than the baseline value to be considered a PCS finding. A separate listing will be provided that presents all vital sign values for the subjects meeting PCS criteria during treatment.

8.0 Analysis Conventions

Baseline

The baseline value refers to the last non-missing measurement collected before the first dose of study drug is received. The protocol operations manual specifies that all Day 1 baseline procedures are to be performed prior to administering the first dose of study drug. Therefore, all Day 1 assessments for which time is not collected will be assumed to be pre-dose and the baseline value will be the last non-missing measurement collected on or before the first day of study drug administration.

All Day 1 assessments with time available must be before the time of first dose to be considered baseline and the last non-missing measurement collected before the date and time of the first dose of study drug will be considered the baseline value. If multiple measurements that are prior to dosing are recorded on the same date and with the same time or if time is not available, then the average of these measurements will be considered the baseline value. The same baseline value will be used for analyses of the Treatment and Post-Treatment Periods.

Safety assessments that are related to a serious adverse event that occurred on the first dose day are excluded when applying this algorithm.

Study Days

Study days are calculated for each time point relative to the first dose of study drug. Study days are negative values when the time point of interest is prior to the first study drug dose day. Study days are positive values when the time point of interest is after the first study drug dose day. There is no Study Day 0. Study Day 1 is the day of the first dose of study drug.

Study Drug End Days (Days Relative to the Last Dose of Study Drug) are calculated for each time point relative to the last dose of study drug. The last day of study drug dosing is defined as Study Drug End Day 0. Days before it have negative study drug end days and days after it have positive study drug end days.

The **Final Treatment Value** is defined as the last non-missing measurement collected after Study Day 1 and on or before Study Drug End Day 2. The **Final Post-Treatment Value** for each subject is the last non-missing measurement collected after Study Drug End Day 2 and on or before Study Drug End Day 999.

Definition of Analysis Windows

For efficacy analyses of HCV RNA and resistance, the time windows specified in [Table 3](#) and [Table 4](#) describe how efficacy data are assigned to protocol-specified time points during the Treatment and Post-Treatment Periods, respectively. All time points and corresponding time windows are defined based on the date/time of blood sample collection.

For laboratory data and vital signs, the time windows specified in [Table 3](#) and [Table 5](#) describes how data are assigned to protocol specified time points.

If more than one assessment is included in a time window, the assessment closest (except in analyses of SVR) to the nominal time will be used. If there are two observations equally distant to the nominal time, the latest one will be used in analyses. For analyses of SVR (e.g., SVR₁₂), the last value in the window will be used.

If multiple measurements are made on the same day for a safety laboratory parameter or a vital sign parameter, the average of the values will be used to calculate descriptive statistics and in analyses of the mean change from baseline. For summaries of shifts from baseline and potentially clinically significant values, multiple values on the same day will not be averaged; all values will be considered for these analyses.

Table 3. Analysis Time Windows for HCV RNA, Resistance Endpoints, Laboratory, Vital Sign Measurements, and PRO Instruments (Treatment Period)

Scheduled Visit	Nominal Day (Study Day)	Time Window (Study Day Range)
Day 1/Baseline ^a	1	≤ 1 ^a
Week 4	28	2 to 42
Week 8	56	43 to 70
Final Treatment Visit ^b	2 to ≤ 2 days after last dose of study drug	

a. Day of first dose of study drug.

b. The last value within the window will be used to define the Final Treatment Visit value. The upper bound of this Final window is Study Drug End Day ≤ 2.

Note: Data must also have Study Drug End Day ≤ 2 for all windows. The result closest to the scheduled time point will be used.

Table 4. Analysis Time Windows for HCV RNA and Resistance Endpoints (Post-Treatment Period)

Scheduled Visit ^a	Nominal Day (Study Drug End Day)	Time Window (Study Drug End Day Range)
Post-Treatment Week 4	28	3 to 56
Post-Treatment Week 12	84	57 to 126
SVR ₄ ^b	28	3 to 56
SVR ₁₂ ^b	84	57 to 126

a. Post-Treatment Visits are applicable to subjects who received at least one dose of study drug.

b. For SVR windows, the last value in the window will be used.

Note: The result closest to the scheduled time point will be used, except for SVR₄ and SVR₁₂. Data must also have Study Drug End Day > 2 for all windows. Study Drug End Day 0 is defined as the day of the last dose of study drug.

Table 5. Laboratory Data, Vital Sign and PRO Instruments Visit Windows (Post-Treatment Period)

Scheduled Time	Nominal Day (Study Drug End Day)	Time Window (Study Drug End Days Range)
Post-Treatment Week 4	28	3 to 56
Post-Treatment Week 12	84	57 to 126
Final Post-Treatment Visit ^a	> 2 days after the last dose of study drug	

a. The last value within the Post-Treatment Period window will be used to define the final post-treatment value. The lower bound of this Final window is Study Drug End Day 3.

Note: The result closest to the scheduled time point will be used. Data must also have Study Drug End Day > 2. Vital signs and hematology, chemistry, urinalysis, and coagulation panels are collected at both post-treatment visits. PRO instruments are collected at PTW12/PTDC only.

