5.0 Analysis Populations and Important Subgroups

5.1 Analysis Populations

The modified Intention-to-Treat (mITT) population includes all enrolled subjects who received at least 1 dose of study drug, excluding subjects who did not achieve SVR₁₂ for reasons other than virologic failure. The mITT population will be used for the primary efficacy analysis.

The Intention-to-Treat (ITT) population includes all enrolled subjects who received at least 1 dose of study drug. The ITT population will be used for all secondary and exploratory efficacy analysis as well as for baseline analyses.

The Safety Population consists of all subjects who received at least 1 dose of study drug.

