6.0 Efficacy Analyses

6.1 General Considerations

Plasma HCV RNA levels will be determined for each sample collected by the central laboratory using the Roche COBAS[®] AmpliPrep/COBAS[®] TaqMan[®] HCV Quantitative Test, v2.0. The lower limit of detection (LLOD) and lower limit of quantification (LLOQ) for this assay (regardless of genotype) are both 15 IU/mL.

HCV RNA results that are detectable but not quantifiable are reported as "< 15 IU/ML HCV RNA DETECTED" and those that are undetectable are reported as "HCV RNA NOT DETECTED" in the database.

The notation "HCV RNA < LLOQ" is used to represent all HCV RNA values < 15 IU/mL, including values reported as "HCV RNA NOT DETECTED" or "< 15 IU/ML HCV RNA DETECTED." HCV RNA \geq LLOQ are all quantifiable values of 15 IU/mL or greater.

Definitions for Efficacy Endpoints

A confirmed quantifiable value during treatment is defined as any two consecutive HCV RNA measurements \geq LLOQ (or 100 IU/mL for **Breakthrough**), either both during treatment or at the final treatment measurement and the next consecutive post-treatment measurement. A confirmed quantifiable post-treatment value is defined as any two consecutive post-treatment HCV RNA measurements \geq LLOQ.

Breakthrough = confirmed HCV RNA \geq 100 IU/mL after HCV RNA < LLOQ during the Treatment Period; or confirmed increase from nadir in HCV RNA (two consecutive HCV RNA measurements > 1 log₁₀ IU/mL above nadir) at any time point during the Treatment Period. A single breakthrough value (\geq 100 IU/mL or > 1 log₁₀ above nadir) followed by lost to follow-up also will be considered a breakthrough (i.e., will not require confirmation).

EOT failure = HCV RNA \geq LLOQ at end of treatment with at least 6 weeks of treatment, where the HCV RNA value must be collected on or after Study Drug Day 36 and study drug duration \geq 36 days.

On-treatment virologic failure = **Breakthrough** or **EOT failure**.

SVR₄ = HCV RNA < LLOQ in the SVR₄ window (4 weeks after the last actual dose of study drug) without any confirmed quantifiable (\geq LLOQ) post-treatment value before or during that SVR window.

SVR₁₂ = HCV RNA < LLOQ in the SVR₁₂ window (12 weeks after the last actual dose of study drug) without any confirmed quantifiable (\geq LLOQ) post-treatment value before or during that SVR window.

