Post-treatment relapse (i.e., **Relapse₁₂**) = confirmed HCV RNA \geq LLOQ between end of treatment and 12 weeks after last actual dose of study drug (up to and including the SVR₁₂ assessment time point) for a subject with HCV RNA $<$ LLOQ at Final Treatment Visit who completed treatment (defined as study drug duration \geq 52 days), excluding reinfection.

Virologic failure = On-treatment virologic failure or Post-treatment relapse (Relapse₁₂)

Only subjects who have at least one post-treatment HCV RNA value will be included in the analysis of relapse. For the analysis of relapse, completion of treatment is defined as any subject with study drug duration of 52 days or greater. If the last available post-treatment value is \geq LLOQ, then the subject will be considered a relapse (i.e., will not require confirmation).

HCV reinfection is defined as confirmed HCV RNA \geq LLOQ after the end of treatment in a subject who had HCV RNA $<$ LLOQ at Final Treatment Visit, along with the post-treatment detection of a different HCV genotype, subtype, or clade compared with baseline, as determined by phylogenetic analysis of the NS3 or NS5A, and/or NS5B gene sequences. Reinfection in the case of the same HCV subtype is defined as a clade switch, as indicated by the lack of clustering between the baseline and post-treatment sequences by phylogenetic analysis. If phylogenetic analysis is not possible due to technical difficulties, HCV reinfection may be determined with a confirmed HCV genotype or subgenotype switch by the Versant HCV Genotype Inno-LiPA Assay v2.0 or Sanger assay.

Reasons for SVR₁₂ Non-Response

Subjects who do not achieve SVR₁₂ (SVR₁₂ non-responders) will be categorized as having:

1. On-treatment virologic failure (see **On-treatment virologic failure** definition);

2. Relapse (defined according to the **Relapse₁₂** definition for subjects who complete treatment);
3. Prematurely discontinued study drug with no on-treatment virologic failure (defined as any SVR₁₂ non-responder who prematurely discontinued study drug [study drug duration < 52 days] and did not meet the **On-treatment virologic failure** or **Relapse₁₂** definition);
4. HCV reinfection (see definition described earlier);
5. Missing follow-up data in the SVR₁₂ window (defined as any subject who completed study drug without data in the SVR₁₂ window after applying the imputation rules and not meeting the definitions of [1], [2], [3], or [4]);

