6. Other (defined as any SVR₁₂ non-responder not meeting the definitions of [1] – [5]).

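### A completer who is quantifiable at Week 4, has no valid end-of-treatment HCV RNA sample and is viremic afterwards is classed as Other and leaves the primary mITT analysis

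*SAP*

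**What the plan says.** **Sampling.** After Day 1, the activity schedule (protocol Appendix D) has on-treatment HCV RNA at Week 4 (Day 28) and Week 8 (Day 56) only.

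**Final Treatment value.** SAP 8.0 defines it as the "last non-missing measurement collected after Study Day 1 and on or before Study Drug End Day 2". The notes to the window tables agree. For the treatment period (Table 3), "Data must also have Study Drug End Day ≤ 2 for all windows". For the post-treatment period (Table 4), "Data must also have Study Drug End Day > 2 for all windows". A sample on Study Drug End Day 3 or later is therefore a post-treatment sample, whatever visit it was meant for.

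**Outcome definitions (SAP 6.1).**
- Relapse₁₂ applies only to a subject with HCV RNA < "LLOQ at Final Treatment Visit who completed treatment", with completion meaning at least 52 days of study drug.
- End-of-treatment failure carries a timing condition, "where the HCV RNA value must be collected on or after Study Drug Day 36".
- Virologic failure is on-treatment failure (breakthrough or end-of-treatment failure) or Relapse₁₂, and nothing else.
- Non-responders who fit none of reasons 1 to 5 go to reason 6, Other.

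**Primary population (SAP 5.1; same rule in protocol 7.2).** The mITT is formed by "excluding subjects who did not achieve SVR₁₂ for reasons other than virologic failure".

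**The concern.** The relapse and end-of-treatment failure definitions are meant to cover, between them, a completer whose virus persists or returns. They leave a gap. The Final Treatment value may be as old as Week 4, but the end-of-treatment failure rule refuses a value that old. A subject whose only on-treatment value is a quantifiable Week 4 result is not negative enough to relapse and was not sampled late enough to fail at end of treatment.

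Because the mITT removes every non-responder who is not a virologic failure, the gap takes a failure out of both numerator and denominator of the primary estimate. The error has one direction: mITT SVR₁₂ can only go up, and the secondary relapse count can only go down. The mITT test also opens the fixed sequence to the ITT test (SAP 4.6).

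**Working it through.** **1. Following one subject through the rules.** Take a completer with last dose on Day 56, Week 4 = 40 IU/mL, Week 8 below the LLOQ, and quantifiable HCV RNA at Post-Treatment Weeks 4 and 12. Suppose the Week 8 sample is drawn on Day 59 (End Day 3).

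- Final Treatment value: Week 4, 40 IU/mL.
- Relapse₁₂: not met, because the Final Treatment value is ≥ 15 IU/mL.
- End-of-treatment failure: not met, because Day 28 is before Day 36.
- Breakthrough: not met, because there is no earlier on-treatment value below the LLOQ and no rise of more than 1 log₁₀ above nadir.
- Premature discontinuation: not met, because duration is at least 52 days.
- Reinfection: not met, because it also requires HCV RNA below the LLOQ at the Final Treatment Visit.
- Missing SVR₁₂ data: not met, because the window has a value.
- Result: Other, excluded from the mITT.

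**2. Varying the timing and the Week 4 value.**

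| Week 4 | Last dose | Week 8 sample | End Day | Class |
|---|---|---|---|---|
| 40 | Day 56 | Day 56, < LLOQ | 0 | Relapse |
| 40 | Day 56 | Day 58, < LLOQ | 2 | Relapse |
| 40 | Day 56 | Day 59, < LLOQ | 3 | Other |
| 40 | Day 56 | Day 63, < LLOQ | 7 | Other |
| 40 | Day 53 | Day 56, < LLOQ | 3 | Other |
| 40 | Day 52 | Day 56, < LLOQ | 4 | Other |
| 40 | Day 56 | missing | – | Other |
| 40 | Day 56 | Day 59, 200 IU/mL | 3 | Other |
| < 15 | Day 56, 53 or 52 | any of the sampling days above, < LLOQ | 0 to 7 | Relapse |

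Sampling time alone moves the same subject in or out of the primary analysis. The visit need not be late: a last dose on Day 52 or 53 still counts as completion, and an on-schedule Day 56 sample is then End Day 4 or 3. The protocol's 2-day sampling limit (5.6) is stated for the premature discontinuation visit. None is stated for a completer's Week 8 visit.

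**3. The plan's own figure.** Inputs from SAP 4.4: n = 230, threshold 92.4%, assumed SVR₁₂ 98% in 184 non-GT3 and 94% in 46 GT3 subjects.

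- Weighted rate: 0.8 × 98% + 0.2 × 94% = 97.2%.
- Power with the null variance in the critical value: Φ{[(0.972 − 0.924) − 1.96√(0.924 × 0.076/230)] / √(0.972 × 0.028/230)} = 89.7%. This matches the stated 90%.
- The interval rule actually planned in SAP 6.2 has exact binomial power of 97.1%.

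**4. The decision boundary.** With five or more non-responders, the lower limit is p − 1.96√(p(1 − p)/n).

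- 11 failures in 230: 0.95217 − 1.96 × 0.01407 = 92.46%, met.
- 12 failures in 230: 0.94783 − 1.96 × 0.01466 = 91.91%, not met.
- The same 12, one dropped as Other, so 11 in 229: 0.95197 − 1.96 × 0.01413 = 92.43%, met.

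**5. How many subjects.** The documents give neither input, so these are assumptions: 5% to 20% of Week 8 samples late or missing, and 5% to 25% of subjects quantifiable at Week 4.

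- Subjects in the gap, if the two are independent: 230 × 0.05 × 0.05 = 0.6 up to 230 × 0.20 × 0.25 = 11.5.
- Failures lost at the design failure rate of 2.8%: 0.02 to 0.3.
- If slow responders failed at 10% (also an assumption), the top of the range is 11.5 × 0.10 = 1.15.

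**6. Effect on the decision.** Under the design rates, with each failure in the gap with probability 0.25% (0.05 × 0.05) to 5% (0.20 × 0.25), the chance that this route turns a miss into a success is about 0.05% to 0.76%. At a true rate of exactly 92.4%, the chance of meeting the criterion is 6.2% with no failures dropped, 6.6% with 1% dropped and 8.3% with 5% dropped.

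**The case against.** **Three things must coincide:** no valid end-of-treatment sample, a quantifiable Week 4 value, and treatment failure. This stands. A reader might infer that any late Week 8 sample loses a relapse. It does not: with Week 4 below the LLOQ, every case tested is still a relapse.

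**The size is unknown.** This stands too. The Operations Manual, which may set visit tolerances, is not among the documents. A reader might also infer that slow responders fail more often, or that the primary result is materially biased. The documents give no figure for the first. At the design failure rate the expected loss is well below one subject, so the second is not supported either.

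**Other parts of the plan catch it.** In part. The subject stays a failure in the ITT SVR₁₂ analysis, and SAP 6.2 lists non-responders by reason and subjects excluded from the mITT. The planned Wilson sensitivity analysis gives a lower limit of 91.6% for 11 in 229, so a borderline pass would already look fragile. None of this corrects the primary estimate or the relapse count.

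**The last-available-value sentence in SAP 6.1 covers it.** It says that a subject whose last post-treatment value is ≥ LLOQ is considered a relapse. Its parenthesis limits it to waiving confirmation, and reason 2 for non-response points back to the Relapse₁₂ definition, so the requirement at the Final Treatment Visit remains.

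**Conclusion.** The gap is real on the text. It needs a completer with no HCV RNA sample between Study Drug Day 36 and Study Drug End Day 2, a Week 4 value at or above the LLOQ, and quantifiable HCV RNA after treatment. It also assumes no unscheduled on-treatment sample that would change the Final Treatment value or establish breakthrough. Such a subject is probably rare, and the design should not be expected to lose even one. The point still deserves action because the stated rule gives a wrong classification, always in the favourable direction, in the primary analysis, and one subject is enough at the boundary (91.91% against 92.43%). Deciding how to class such a subject after the data are seen would be post hoc.

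**What to change.** In SAP 6.1, extend the virologic failure definition. A completer counts as a virologic failure, and so stays in the mITT, if all of the following hold:

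- there is no HCV RNA sample between Study Drug Day 36 and Study Drug End Day 2;
- the Final Treatment value is ≥ LLOQ;
- post-treatment HCV RNA is ≥ LLOQ, confirmed or as the last available value, through the SVR₁₂ window;
- genotype or phylogenetic analysis does not show reinfection.

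Report these subjects under their own reason for non-response. For them, waive the requirement of HCV RNA below the LLOQ at the Final Treatment Visit in the reinfection definition. Otherwise a true reinfection could not be recognised and would be counted as virologic failure.

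Leave Relapse₁₂ unchanged for subjects whose Final Treatment value is below the LLOQ. Barring Week 4 values from serving as the Final Treatment value would be a mistake: completers with a negative Week 4 and no valid Week 8 sample are now correctly counted as relapses and would lose that status.

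The cost is a short addition to the SAP and a programming condition, with no new data. The mITT SVR₁₂ estimate may be slightly less favourable.

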9.0 Summary of Changes

There have been no changes since the latest version of the protocol.

